3.4 Amyloid PET analysis

3.4.1 Amyloid PET substudy

Please refer to the placebo-controlled SAP.

Final V1.0

3.4.2 Amyloid PET regions-of-interest and reference regions

Please refer to the placebo-controlled SAP.

3.4.3 Amyloid PET Analysis Population

Please refer to the placebo-controlled SAP.

3.4.4 By Visit Summary and MMRM Model

All the analyses will be presented by LTE treatment group (early start low dose, early start high dose, late start low dose, late start high dose). The following two comparisons will be evaluated for amyloid PET SUVR in the LTE period:

- The early start low dose compared with the late start low dose;
- The early start high dose compared with the late start high dose.

The baseline and change from baseline amyloid PET SUVR values will be summarized by LTE treatment groups by visit for all the visits in the placebo-controlled and LTE period for each of the target ROIs using cerebellum as the reference region for each of the amyloid PET analysis populations. In addition, the baseline and change from baseline amyloid composite ROI values will be summarized by LTE treatment groups by visit for each reference regions for each of the amyloid PET analysis populations.

For the ¹⁸F-florbetapir amyloid PET analysis population, an MMRM model will be used to analyze change from baseline SUVR for each target ROI with cerebellum as the reference region for all the visits in the placebo-controlled and LTE period. Fixed effects of the model will include LTE treatment groups, visit, treatment group-by-visit interaction, baseline SUVR (continuous), baseline SUVR by visit interaction, baseline MMSE (continuous), laboratory ApoE & status (carrier and non-carrier), and baseline age (continuous). Visit and treatment group will be treated as categorical variables in the model along with their interactions. An unstructured covariance matrix will be used to model the within-patient variance-covariance errors. If the unstructured covariance structure matrix results in a lack of convergence in any of the parameters, the heterogeneous Toeplitz covariance structure followed by the heterogeneous first-order autoregressive covariance structure will be used for all the parameters. The Kenward-Roger approximation will be used to estimate the denominator degrees of freedom. Adjusted means for each treatment group, pairwise adjusted differences for the comparisons, 95% confidence intervals for the differences and associated p-values will be presented at each visit. Visits with too few data may be excluded from the MMRM analysis and be analyzed by ANCOVA instead. The same MMRM model will also be used to analyze the change from baseline SUVR for the composite ROI with each of the reference regions. No multiple comparison adjustment will be used for amyloid PET analysis.

Visit Windows for by visit analyses

Statistical Analysis Plan

Long-Term Extension Period

Final V1.0

For amyloid PET by visit summaries and MMRM models, the analysis visit should be defined using visit windows (see Table 4 below). The rationale is to use the same analysis visit windows as for the efficacy endpoints for the visits that the efficacy endpoints are also collected. Since the visit for the efficacy measurements is on Week 134, while the visit for amyloid PET measurements is on Week 132, the start of the analysis visit window for Week 132 amyloid PET is 2 weeks earlier than that for efficacy, while the same end of the analysis visit window as Week 134 is used to be conservative. If there is more than 1 value in the same analysis visit window (>1 value for the same analysis visit) for a certain parameter for a subject, then the closest record to the target visit day will be used for the by visit analysis. If they are with the same distance from the target visit day, then the record with the later time will be used for the by visit analysis.

Table 4. Visit Windows for amyloid PET data

Analysis visit *	Target visit day	Analysis visit window	
Baseline	1	Most recent non-missing pre-dose value	
Week 26	183	[92, 266]	
Week 78	547	[449, the end day of the placebo-controlled period ¹]	
Week 132	925	[827, 1036]	
Week 182	1275	[1205, 1365]	
Week 260	1821	[1731, 1911]	
Week 338	2367	≥ 2277	

Analysis visit is the visit at which the specific week started.

3.5 **Safety Analyses**

General Considerations

Analysis population

Safety population will be used for safety analyses of AEs, clinical laboratory data, Columbia Suicide Severity Rating Scale (C-SSRS) data, ECG data and vital sign data (all the safety data except for ARIA data). Safety MRI population will be used for analyses of ARIA data.

LTE safety treatment groups

Since all the subjects are supposed to receive active treatment in LTE, the LTE safety treatment groups which are exactly the same as the LTE randomization treatment groups will be used for all the safety analyses. Subjects who were randomized to placebo group but accidentally received one or more doses of the active treatment during the placebo-controlled period will still be classified as late start for all the safety analyses that involves LTE, but their applicable safety data in the placebo-controlled period will be included in the analysis for placebo-controlled and LTE active treatment period.

^{1.} The end day of the placebo-controlled period is the last day before the first infusion in LTE, and is the last day in study for subjects who do not enter LTE.

^{2.} The start day of the LTE period is the day of first infusion in LTE period.

Final V1.0

Safety analysis period

Analysis period will be specified for each output. Safety data in the specified analysis period will be included in the analysis. Listings will include all data in the placebo-controlled and LTE period, unless otherwise specified.

Safety analysis displays

For either analysis period in this SAP (LTE period, placebo-controlled and LTE period, or placebo-controlled and LTE active treatment period), AEs, clinical laboratory data, C-SSRS data, ECG data and vital sign data (all the safety data except for ARIA data) will be summarized by LTE treatment group (late start low dose, late start high dose, early start low dose, early start high dose, and in addition late start total, early start total and BIIB037 total; analysis display A in Appendix 4.1), unless otherwise specified. ARIA tables will be presented by LTE treatment group stratified by ApoE status (3 columns under each of the 4 LTE treatment groups: ApoE ε4+, ApoE ε4- and total, and in addition late start total and early start total; analysis display B in Appendix 4.1), unless otherwise specified. A subset of AE tables will also be presented by LTE treatment group stratified by ApoE status in addition to by LTE treatment group. Listings will be presented by LTE treatment group stratified by ApoE status, with an indicator of the study period (pre-dosing, placebo-controlled, or LTE) for each record when the event/assessment occurred.

LTE baseline for late start subjects

Placebo-controlled baseline is defined as the last non-missing measurement collected prior to the first dose (the baseline used for placebo-controlled period analyses). LTE baseline is defined as the last non-missing measurement collected prior to the first dose of the LTE period. For analyses on the LTE period or on the placebo-controlled and LTE active treatment period, LTE baseline will be used for late start subjects who are assigned to receiving aducanumab in the LTE period. Study day and analysis visit window for analyses using LTE baseline will be derived based on the first day of study drug in LTE.

Incidence, incidence proportion and incidence rate

- Incidence and incidence proportion will be provided in incidence tables. Incidence is
 defined as the number of subjects who experienced an event. Incidence proportion is
 defined as the number of subjects who experienced an event divided by the total number
 of subjects in the analysis population, i.e., percentage. Each subject will be counted only
 once within each category.
- Incidence and incidence rate will be provided in incidence rate tables. Two different kinds
 of incidence rate tables will be provided as appropriate for different analyses. Definitions
 are provided below.

Final V1.0

- (1) Follow-up adjusted incidence rate defined as the number of subjects who experienced an event divided by the total of entire follow-up time among the subjects in the analysis population. The entire follow-up time for a subject is defined as the time from the first dose until the last day on study. Each subject will be counted only once within each category.
- (2) Exposure-adjusted incidence rate (EAIR) defined as the number of subjects who experience an event divided by the total exposure adjusted follow-up time among the subjects in the analysis population. The exposure adjusted follow-up time is defined as the time from the first dose until the initial occurrence of the event for those who experienced an event, or from the first dose until the end of follow-up (the last day on study) for those who did not. Each subject will be counted only once within each category.

3.5.2 Clinical Adverse Events

Treatment-emergent AEs (TEAEs)

All AEs will be analyzed based on the principle of treatment emergence. A treatmentemergent AE was defined as an AE that started or worsened after the start of first infusion of study treatment.

To define treatment emergence for AEs with missing start or stop date or time the following additional criteria will be used:

- if both the start and stop dates for a particular AE are missing, then that AE is considered treatment emergent;
- if the start date for a particular AE is missing and the stop date/time falls after the first dose date/time, then that AE is considered treatment emergent;
- if the start date for a particular AE was the same as the first dose date, and the start time was missing, then that event is considered treatment emergent.

For AEs with a partial start date, the year/month of the event date will be compared to that of the first dosing date to determine whether the event is treatment emergent.

In addition, SAEs that occurred since a subject was screened in the study and prior to the first infusion of study treatment, which by definition are not treatment-emergent, will be analyzed separately.

Only TEAEs will be included in the AE tables, unless otherwise specified. Listings of AEs will include all events, whether treatment-emergent or not.

As specified in the protocol, subjects were expected to return to the study site for an End of Study visit 18 weeks after the last administration of study treatment. However, some subjects may elect to continue study participation on a modified schedule after discontinuing treatment, possibly in substantial excess of 18 weeks. For most general AE summaries, AEs with an onset more than 18 weeks after the last dose will be excluded (will specify in the footnote of the specific table). For incidence rate analyses excluding AEs more than 18 weeks after the last dose, the "last day on study" in follow-up time calculation will be replaced with

Final V1.0

"18 weeks after last dose or last day on study, whichever earlier". Summaries of deaths and AEs leading to study withdrawal, and other selected analyses will include all AEs regardless of the time since the last dose. Listings will include all AEs, unless otherwise specified.

3.5.2.1 Summary and incidence analysis

Overall summary of AE table will be done for the LTE period, as well as for the placebo-controlled and LTE active treatment period presented by LTE treatment group as well as LTE treatment group stratified by ApoE status. The following information will be summarized: the number of subjects with any AE, with any AE by maximum severity, the number of subjects with any related AE (related to study drug as assessed by investigator), the number of subjects with SAE, the number of subjects with related SAE, the number of subjects with AE leading to study drug discontinuation, the number of subjects with AE leading to study withdrawal, and the number of deaths.

The sorting order of AE incidence tables, unless otherwise specified, will be by decreasing frequency order of "BIIB037 total" column within each category in the tables presented by LTE treatment group, and by decreasing frequency order of "BIIB037 early start total" column within each category in the tables presented by LTE treatment group stratified by ApoE status. A subject is counted only once within each category in each table. For example, for the table of AEs by system organ class and preferred terms sorted by decreasing frequency presented by LTE treatment group, system organ class will be presented in decreasing frequency order of BIIB037 total column, and within each system organ class, preferred terms will be presented in decreasing frequency order of BIIB037 total column. A subject is counted only once within each system organ class and preferred term.

The following AE incidence tables will be provided for the LTE period (presented both by LTE treatment group and by LTE treatment group stratified by ApoE status, unless otherwise specified):

- 1. AEs by system organ class and preferred term sorted by decreasing frequency
- 2. AEs by system organ class and preferred term sorted by alphabetical order analysis (by LTE treatment group)
- 3. AEs by system organ class, high level group term and preferred term (by LTE treatment group)
- 4. AEs by system organ class (by LTE treatment group)
- 5. AEs by preferred term
- 6. AEs with an incidence of 5% or more in any treatment group by preferred term
- 7. Severe AEs by system organ class and preferred term
- 8. Severe AEs by preferred term (by LTE treatment group)
- 9. AEs by maximum severity by system organ class and preferred term (by LTE treatment group) (System organ class will be presented alphabetically. Preferred terms will be presented in decreasing frequency order. Maximum severity will be presented within each preferred term in the order of mild, moderate, severe, unknown and total.

Final V1.0

A subject will be counted only once at the maximum severity within each system organ class and preferred term.)

- 10. AEs by maximum severity by preferred term (by LTE treatment group) (Preferred terms will be presented in decreasing frequency order. Maximum severity will be presented within each preferred term in the order of mild, moderate, severe, unknown and total. A subject will be counted only once at the maximum severity within each preferred term.)
- 11. Related AEs by system organ class and preferred term
- 12. SAEs by system organ class and preferred term
- 13. SAEs by preferred term
- 14. Related SAEs by system organ class and preferred term
- 15. AEs that led to discontinuation of study treatment by system organ class and preferred term
- 16. AEs that led to withdrawal from study by system organ class and preferred term
- 17. SAEs with fatal outcome by system organ class and preferred term
- 18. AEs that occurred within 2 hours from infusion start by system organ class and preferred term (by LTE treatment group)

The following listings will be provided for the placebo-controlled and LTE period:

- 1. Listing of AEs
- 2. Listing of SAEs
- 3. Listing of AEs that led to discontinuation of study treatment
- 4. Listing of AEs that led to withdrawal from study
- 5. Listing of AEs that occurred within 2 hours from infusion start
- 6. Listing of AEs related to PET ligands
- 7. Listing of SAEs with fatal outcome
- 8. Listing of AEs for subjects with treatment-emergent positive anti-BIIB037 antibody

3.5.2.2 Incidence and incidence rate analysis for placebo-controlled and LTE active treatment period

Due to the different length of placebo-controlled and LTE active treatment period in early start versus late start subjects, both incidence tables and follow-up adjusted incidence rate tables will be used for AE analyses in this period. The entire follow-up time is from the first dose in active treatment period (first dose in placebo-controlled period for early start subjects and first dose in LTE period for late start subjects) until the last day in the study.

Final V1.0

The following incidence and follow-up adjusted incidence rate tables will be provided for the placebo-controlled and LTE active treatment period (presented both by LTE treatment group and by LTE treatment group stratified by ApoE status, unless otherwise specified):

- 1. AEs by system organ class and preferred term sorted by decreasing frequency
- 2. AEs by system organ class, high level group term and preferred term (by LTE treatment group)
- 3. AEs by preferred term
- 4. Severe AEs by system organ class and preferred term (by LTE treatment group)
- 5. Severe AEs by preferred term
- 6. Related AEs by system organ class and preferred term
- 7. SAEs by system organ class and preferred term
- 8. SAEs by preferred term
- 9. Related SAEs by system organ class and preferred term

3.5.3 ARIA - AE of Special Interest

3.5.3.1 Background

Please refer to the placebo-controlled SAP for details.

3.5.3.2 Incidence and summary of ARIA

Incidence of ARIA-E, ARIA-H, ARIA-E and ARIA-H (not necessarily concurrent), concurrent ARIA-E and ARIA-H, ARIA-E or ARIA-H, isolated ARIA-H (only ARIA-H, no ARIA-E), ARIA-H microhemorrhage, ARIA-H macrohemorrhage and ARIA-H superficial siderosis in the LTE period and in the placebo-controlled and LTE active treatment period will be summarized based on both AE eCRF and MRI data. If there is any discrepancy in incidence between the two data sources, a listing of the subjects and ARIA events with discrepancy will be provided. In addition, the incidence table based on AE eCRF source will also be done by LTE treatment group (analysis display A in Appendix 4.1).

Number of subjects with each type of ARIA, maximum severity and worst symptomatic status of the type of ARIA being analyzed in the LTE period and in the placebo-controlled and LTE active treatment period will be summarized based on AE eCRF. For subjects with symptomatic ARIA, the maximum severity of symptoms will also be summarized.

Summary of concurrent ARIA-E and ARIA-H will be provided including the following information for the LTE period and for the placebo-controlled and LTE active treatment period: number of subjects with concurrent ARIA-E and ARIA-H (and further broken down to each type of ARIA-H), the severity of ARIA-E based on MRI, the symptomatic status of ARIA-E, the severity of symptoms based on AE eCRF. For subjects with recurrent ARIA-E

Final V1.0

events, if there is an event concurrent with ARIA-H, it will be used for the summary, and the first concurrent event will be used if there are more than one event concurrent with ARIA-H.

An incidence table of AEs considered by the investigator to be related to ARIA by system organ class and preferred term for subjects with symptomatic ARIA in the placebo-controlled and LTE active treatment period will be provided, as well as a listing of these AEs. Similarly, an incidence table of AEs related to ARIA for subjects with symptomatic ARIA and severe symptoms will be provided, as well as a listing of these AEs.

Listings of AE records for each type of ARIA events and listings of MRI assessments for subjects with each type of ARIA events will be provided.

Montreal Cognitive Assessment (MOCA) is performed at baseline, Week 80 (the first visit in LTE) and each unscheduled ARIA monitoring visit for ARIA subjects (approximately every 4 weeks) except for mild asymptomatic microhemorrhage subjects. An incidence table of late start subjects with ARIA events only in the LTE period (no ARIA in the placebo-controlled period) whose MOCA total scores decrease 2 points or more from Week 80 will be provided. Since Week 80 MOCA was not a planned study event until protocol version 4, some subjects may not have a Week 80 MOCA score. For these subjects, their Week 80 MOCA will be imputed as their baseline MOCA plus the mean change from baseline at Week 80 from subjects who have a Week 80 MOCA and did not experience any ARIA in the placebo-controlled period within each treatment group and ApoE status. A listing of MRI assessments and MOCA total score for subjects with ARIA events in either placebo-controlled or LTE period will be provided.

3.5.3.3 Summary of recurrent ARIA-E

Follow-up adjusted incidence rate of subjects with ARIA-E, with 2 or more events of ARIA-E, with 3 or more events of ARIA-E and with more than 3 events of ARIA-E over their entire follow-up time for the placebo-controlled and LTE active treatment period will be summarized based on AE eCRF.

Number of total ARIA-E events in the placebo-controlled and LTE active period and the MRI severity of each event will be summarized based on AE eCRF. Number of symptomatic ARIA-E events in the placebo-controlled and LTE active period, and the severity of the symptoms of each symptomatic event will be summarized based on AE eCRF.

Summary of first ARIA-E events table based on AE eCRF will summarize the number of subjects with a first event of ARIA-E, the MRI severity of the events, the symptomatic status of the events, the severity of the symptoms for symptomatic events, whether SAE or not, number of resolved and unresolved events, duration of the resolved events, time from first active infusion in study to onset, number of doses received since the start of the period to onset, dose level of the last infusion received prior to onset, dosing status (continue as planned, dose interrupted, dose reduced, or dose discontinued) after the events, and the number of subjects with recurrent ARIA-E events. This table will be done on the placebocontrolled and LTE active treatment period. The same summary of first ARIA-E events table will also be done on the subset of subjects who had recurrent ARIA-E events.

Summary of recurrent ARIA-E events table based on AE eCRF will summarize the following information for both the second and third event of ARIA-E events: the number of subjects CONFIDENTIAL

Final V1.0

with the previous event of ARIA-E, the number of subjects with at least one dose and one MRI after the previous ARIA-E resolution, the number of subjects with this event of ARIA-E, the MRI severity of the events, the symptomatic status of the events, the severity of the symptoms for symptomatic events, whether SAE or not, number of resolved and unresolved events, duration of the resolved events, time from first infusion in study (active or placebo) to onset, time from previous resolution to onset, number of doses received since the start of the period to onset, dose level of the last infusion received prior to onset, dosing status (continue as planned, dose interrupted, dose reduced, or dose discontinued) after the events. The number of subjects with more than 3 events of ARIA-E, and the number of subjects who discontinued study treatment after recurrent ARIA-E onset will also be summarized. This table will be done on the placebo-controlled and LTE active treatment period.

A listing of subjects who withdrew from the study with unresolved ARIA-E or subjects with ongoing ARIA-E at the time of data cutoff (also considered as unresolved) will be provided with the details of the event including the duration from onset to last follow-up.

For subjects with recurrent ARIA-E, a listing of study drug administration, MRI assessments, severity and symptomatic status of each event, and end-of-treatment reason (if present) will be provided.

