Table 2: Dosing Scheme for Aducanumab by Treatment Group and ApoE ε4 Carrier Status: Long-Term Extension Period

Doses (every 4 weeks)		1	2	3	4	5	6	7- EOS	
LTE Treatment Group	LTE Treatment Group Stratified by ApoE Status ¹	Dose (mg/kg)							
Early Start High	Early Start High Dose – ApoE ε4 (+)	10							
Dose	Early Start High Dose – ApoE ε4 (-)	10							
Early Start Low	Early Start Low Dose – ApoE ε4 (+)	3							
Dose	Early Start Low Dose – ApoE ε4 (-)	6							
Late Start High	Late Start High Dose – ApoE ε4 (+)	1	1	3	3	6	6	10	
Dose	Late Start High Dose – ApoE ε4 (-)	1	1	3	3	6	6	10	
Late Start Low	Late Start Low Dose – ApoE ε4 (+)	1 1 3							
Dose	Late Start Low Dose – ApoE ε4 (-)	1	1	3	3	3	3	6	

¹ ApoE ε4 status recorded in the Interactive Voice/Web Response System (IXRS).

[figure not shown]
Individual dose adjustments may be implemented in subjects who develop amyloid related imaging abnormalities (ARIA). See Protocol Section 7.2.1.

The total duration of study participation for each subject only participating in the placebo-controlled period of the study will be up to approximately 102 weeks, including a series of screening visits within 8 weeks before administration of the first dose, a 76-week placebo-controlled treatment period, and a safety follow-up (FU) period of approximately 18 weeks after the final dose. The total duration of study participation for each subject participating in the placebo-controlled period and the LTE period will vary and be up to approximately 362 weeks, including a series of Screening visits within 8 weeks before administration of the first dose, a 76-week placebo-controlled treatment period, a 4-week FU period, a 256-week aducanumab dose-blind treatment period, and a safety FU period of approximately 18 weeks after the final dose.

Investigators, study site staff (except for the designated unblinded pharmacist/technician), and study subjects will be blinded to the subjects' randomized treatment assignment for the placebo-controlled period. During the LTE period, investigators and subjects will remain blinded to the treatment assignment in the placebo-controlled period and the aducanumab dose for the LTE period.

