3.1.2 Analyses period

Depending on the purpose, different analyses will be conducted on the following study periods:

- 1. LTE period. Only data in the LTE period will be included in these analyses. For example, incidence table of adverse events in the LTE period.
- 2. Placebo-controlled and LTE period. All the data in the placebo-controlled and LTE periods will be included in these analyses. For example, mean plot of actual laboratory values in the placebo-controlled and LTE period.
- 3. Placebo-controlled and LTE active treatment period. Active treatment period is defined as the study period(s) that a subject is assigned to aducanumab. For early start subjects subjects who are assigned to aducanumab in both placebo-controlled and LTE period, all the data (placebo-controlled and LTE periods) will be included in the analyses. For late start subjects subjects who are assigned to aducanumab in the LTE period, only data in the LTE period will be included. For example, incidence table of adverse events in the placebo-controlled and LTE active treatment period.

Final V1.0

Subjects to be included in a certain output is determined by both the analysis population and the analysis period. For example, the incidence table of adverse events in the LTE period will include subjects in the safety population for the LTE period, i.e., all randomized subjects who received at least one dose of study treatment in the LTE period. The incidence table of adverse events in the placebo-controlled and LTE active treatment period will include subjects in the safety population for the active treatment period, i.e., all randomized subjects who received at least one dose of study treatment in the active treatment period. In this SAP we do not separately define the analysis population in each analysis period.

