3.5.3.5 Time to event analysis

Kaplan-Meier plot of time to first ARIA-E event will be produced based on safety MRI data for the placebo-controlled and LTE active treatment period. Only ARIA-E events that occurred during this period will be included. Time to event is calculated as date of the MRI assessment that initially detects the ARIA-E event - date of the first active infusion +1. Censor time for subjects without ARIA-E is calculated as date of the last MRI assessment in the study - date of the first active infusion +1. Estimated proportion with ARIA-E and number of subjects at risk at selected timepoints will also be presented. The plot will be presented by LTE treatment group stratified by ApoE status.

Final V1.0

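### The LTE table of recurrent ARIA-E counts onset from the first infusion of any kind, not the first active infusion, which shifts late-start onset times by about 80 weeks

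*SAP*

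**What the plan says.** LTE SAP 3.5.3.3 describes two companion tables based on the AE eCRF.

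- **First ARIA-E events:** the timing items are "time from first active infusion in study to onset, number of doses received since the start of the period to onset".
- **Second and third ARIA-E events:** the timing items include "time from first infusion in study (active or placebo) to onset, time from previous resolution to onset", followed by a dose count from the start of the period. On scope the plan says "This table will be done on the placebo-controlled and LTE active treatment period". The first-event table is given the same period.

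LTE SAP 3.1.2 defines that period. Early-start subjects contribute data from both study periods. Late-start subjects contribute LTE data only.

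The other origins stated for this period are:

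- **AE follow-up time (3.5.2.2):** "first dose in placebo-controlled period for early start subjects and first dose in LTE period for late start subjects".
- **Exposure-adjusted ARIA-E rate (3.5.3.4):** the first active dose.
- **Kaplan-Meier time to first ARIA-E (3.5.3.5):** counted from the "date of the first active infusion +1" day.

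The placebo-controlled SAP, section 4.5.3.3, uses the any-infusion origin in both its first-event and its recurrent-event tables, so no mismatch arises there.

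**The concern.** For a late-start subject the first infusion in the study is saline. The recurrent table therefore starts its clock outside its own analysis period and at a different date from its companion table. The LTE SAP gives no reason for this. Its first-event wording differs from the placebo-controlled SAP on both the time origin and the dose count, whereas its recurrent-event wording differs only on the dose count. That pattern suggests an incomplete adaptation rather than a choice.

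ARIA is the adverse event of special interest, and late-start subjects go through titration in the LTE. Elapsed time on drug is one of the things a reader will look at to see when recurrences occur. The first-event table is also to be repeated for the subset with recurrences, so the same subjects' first and later onsets will be read together, on clocks that start about 80 weeks apart.

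**Working it through.** **Inputs**

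- LTE SAP 2.1 gives the schedule as "a 76-week placebo-controlled treatment period, a 4-week FU period, a 256-week aducanumab dose-blind treatment period", preceded by up to 8 weeks of screening and followed by about 18 weeks of safety follow-up, about 362 weeks in total.
- LTE SAP 2.1: 20 placebo-controlled doses, one every 4 weeks.
- LTE SAP 3.5.3.2: Week 80 is the first LTE visit.
- LTE SAP Table 2: late-start subjects in the high-dose group receive dose 7, the first at target, after six titration doses.

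**Step 1. Reproduce the plan's own figures.**
Last placebo-controlled dose: (20 − 1) × 4 = Week 76.
First LTE dose: 76 + 4 = Week 80, which agrees with the stated first LTE visit.
Total participation: 8 + 76 + 4 + 256 + 18 = 362 weeks, which agrees with the stated total.

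**Step 2. Difference between the two origins.**
Shift = (week of first active infusion) − (week of first infusion of any kind).
Early start: 0 − 0 = 0 weeks.
Late start, as scheduled: 80 − 0 = 80 weeks.
Placebo subject accidentally given active drug at week *w* of the placebo-controlled period: *w* − 0 = *w* weeks, with *w* between 0 and 76. LTE SAP 3.5.1 keeps such subjects classified as late start.

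**Step 3. Effect on tabulated late-start values (shift of 80 weeks).**

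| Weeks from first active infusion to recurrence | Tabulated as written | Tabulated with active origin |
|---|---|---|
| 12 | 92 | 12 |
| 20 | 100 | 20 |
| 30 | 110 | 30 |
| 52 | 132 | 52 |

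The onset times are illustrative. With uninterrupted dosing, late-start high-dose titration lasts until dose 7, at (7 − 1) × 4 = 24 weeks after the first active infusion. The 12- and 20-week rows would thus be events during titration that appear at 92 and 100 weeks. Early-start subjects with the same time on drug would appear at 12 and 20.

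**Step 4. Which items and columns are touched.**
Only the time-since-first-infusion item changes. The dose count runs from the start of the period, the last dose level is a fact about one infusion, and time from previous resolution has its own origin. LTE SAP 3.5.1 and display B in the appendix give late-start columns with a late-start total and, on a separate page, early-start columns with an early-start total. The affected cells are the late-start columns and the late-start totals.

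**The case against.** The strongest reply is that the label states its origin openly, so the value is less useful rather than hidden, and that the table answers the titration question better elsewhere. Dose count and last dose level show directly whether a recurrence fell in titration or at target dose. A listing of drug administration and MRI assessments is planned for every subject with recurrent ARIA-E. All of this stands, and it limits the harm. It does not explain why companion tables on one period should use different origins, nor does it make the late-start values comparable with anything beside them.

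A reader might infer four stronger points, which the document does not support:

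- **Pooled totals are distorted.** Display B has no column combining early and late start. The combined column belongs to display A, which for ARIA is specified only for the eCRF incidence table.
- **A planned comparison is invalid.** Early- versus late-start comparisons are defined for efficacy (3.3.1) and amyloid PET (3.4.4), not for ARIA-E timing. No test, rate or decision uses this item.
- **The dose count contradicts the onset time.** They are separate items with separately stated origins. They differ in start point and do not conflict logically.
- **Every late-start event moves by exactly 80 weeks.** That is the scheduled gap. Visit timing varies, and accidental active dosing shortens it.

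**Conclusion.** The inconsistency is real and lies within one section. Followed as written, the recurrent-event table reports late-start onset times about 80 weeks longer than time since first active infusion, and leaves early-start times unchanged. The late-start entries cannot be read beside the early-start columns or the first-event table. The consequence is confined to one descriptive item, for second and third events, in the late-start columns and their totals. The first-event timing, the exposure-adjusted rate and the Kaplan-Meier plot already use the active origin.

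The size rests on the scheduled 76-week treatment period and 4-week follow-up. It also rests on the reading that the first-event table shows the intended origin, which every other origin found for this period supports.

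**What to change.** In the recurrent-event table of LTE SAP 3.5.3.3, replace the any-infusion origin with the origin used in the first-event table of the same section, so that time to onset is counted from the first active infusion in the study. If time since the first infusion of any kind is also wanted, keep it as a separately labelled item next to the active-origin one.

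The cost is one phrase and one derived variable. No new data are needed, early-start values do not change, and no dosing or ARIA management rule is touched.
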